1.3.2 Specific Objectives

- I. To assess barriers, enablers of adherence for ART among Youth in Kiryandongo at baseline and study end.
- II. To assess acceptability of mHealth for ART adherence among Youth in Kiryandongo at baseline and study end
- III. To evaluate effect of the mHealth CFLU tool on ART adherence at months 6 and 12
- IV. To evaluate the cost of the mHealth CFLU tool in comparison to standard of care at 12 months
- V. To assess knowledge of COVID-19 among youths in rural setting

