2.6 Hypotheses and Research Questions

[figure not shown]
1. What is the acceptability of mHealth among YLWH at three (03) of Kiryandongo District HIV Centres, and what are the barriers, facilitators/enablers of ART and clinic visit adherence?

Hypothesis: YLWH will have a high acceptability for mHealth with 70% accepting to use mHealth.

2. What is the effect of the mHealth-CFLU tool on ART adherence among YLWH?

Hypothesis: More than 79% of YLWH using the mHealth-CFLU tool will be adherent to ART (using viral load suppression as a proxy measure for ART adherence we anticipate an increment of 15%).

3. What is the cost of the mHealth CFLU intervention compared to standard of care over a 12 month period?

Hypothesis: mHealth will be cost effective by increasing proportion in care and proportion with viral suppression compared to standard of care

CHAPTER THREE: METHODS

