The Adult Care and Treatment Package includes the following services:(U. MoH, September 2014)

1. HIV counseling and testing
2. HIV prevention services
3. Nutritional Counseling and support
4. Opportunistic infection screening and management
5. Screening and management of non-communicable diseases
6. Diagnostics and laboratory monitoring
7. Sexual and reproductive health
8. Counseling and Psychosocial support
9. ARV preparation, initiation and monitoring
10. Adherence and retention into care
11. Palliative care
12. Mental health

[figure not shown]
[figure not shown]

Fig 5: Study Schema

The outcome variables include:

- ART adherence scores at 6 and 12 months, as assessed by HIV Care Card for those on SoC arm and Self- reported adherence to ART as depicted on the mHealth dash board.
- Viral load suppression at 6 and 12 months, as test results from blood collected at months 6 and 12 with time to viral suppression.
- Retention rates at 6 and 12 months with time to loss to follow-up
- Stigma scores at study start and end

Data Management Analysis Plan

Data collected on paper CRF will be entered using Research Electronic Data Capture software (REDCap) which is a safe, secure, HIPAA-compliant, web-based application and facilitates offline and online data entry. Data will be exported to STATA 14.0, for analysis. Data will then be backed up and archived in both soft and hard copy to avoid losses. The data collected will be stored securely under lock and key to maintain patient confidentiality.

Data regarding call details in the system will be extracted from CFL tool database, exported into Stata for analysis.

[figure not shown]
Visit dates will be extracted from database and proportions lost to follow-up drawn and time to loss to follow-up estimated. Viral load results will be extracted and time to viral suppression with survival analysis curves drawn for both arms.

Data from the MoH HIV card regarding the ART regimen and start dates will be transcribed to the data collection tool and later entered on the REDCap system.

General data analysis

Data will be analyzed at three levels, first at the univariate level, then at the bivariate level and lastly at the multivariate level. A consort diagram will be drawn to show the screening, enrolment, randomization, follow-up and analysis flow of the study.

Univariate Analysis

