Descriptive analysis will be done for the factors that influence adherence, virological suppression, stigma and retention in care. In addition, the distribution of the independent variables will be done with categorical data summarized using frequencies and percentages. Numerical data will be summarized using means and standard deviations for normally distributed data, and median and inter-quartile range for data that is not normally distributed.

Bivariate Analysis

The relationship between independent variables (age, gender, ART duration, marital status, education status, occupation and religion) and adherence and virological suppression will be analyzed using bivariate analysis made using cross tabular analysis and associations investigated using the Pearson Chi-square test.

The Chi-square test is based on the computational formulae below:

$$\chi^2 = \sum_{i=1}^r \sum_{j=1}^c \frac{(O_{ij} - E_{ij})^2}{E_{ij}}$$

Where

r is the number of categories of the ith explanatory variable

c is the number of categories of the dependent variable

[figure not shown]
O_{ij} is the observed number of observations in the ith explanatory

and jth dependent variable

E_{ij} is the expected number of observations in the ith explanatory?

and jth dependent variable

Further, odds ratios shall be used to analyze the relationship between the dependent variable and the independent variables. Variables found to be significant at p value of p ≤ 0.05 will be considered for the multivariable analysis.

Multivariate Analysis

Multivariable logistic regression will be used to determine the factors that influence adherence or virological suppression and retention in care. Variables found to be statistically significant at $p \leq 0.05$ in bivariate analysis and those considered to have a scientific explanation will be entered into the multivariable model.

The multivariate logistic regression adopted is based on the formulae below:

$$\ln \left[\frac{p_i}{1 - p_i} \right] = \beta_0 + \beta_1 X_1 + \dots + \beta_n X_n$$

[figure not shown]
Where;

X = independent variables

p_i = Probability of being adherent and virally suppressed

$1 - p_i$ = Probability of non-adherence or not suppressed virologically

β_0 = constant ; β_i = coefficient of the determinant

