The study findings will be reported as odds ratios, confidence interval and independent variables found to have p value ≤ 0.05 at 95% confidence interval will be considered to be statistically significant in the final model.

[figure not shown]
After the final model, significant factors for ART adherence/ viral suppression will be computed.

Data Monitoring Committee:

The DMC will consist of 3 independent members with expertise in relevant clinical specialties, their responsibility is to ensure that the safety of study subjects is protected while the scientific goals of the study are being met. The previous CFL-RCT at IDI, had no major safety issues and neither were there any gender-based violence, so the DMC will suffice and will be involved in:

- Review the research protocol and plan for data safety and monitoring.

- Evaluate the progress of the trial, including periodic assessments of data quality and timeliness, participant recruitment, accrual and retention, participant risk versus benefit, performance of the trial site, and other factors that can affect study outcome.
- Make recommendations to the PI about continuation, termination, or other modifications of the trial based on the observed beneficial or adverse effects of the intervention under study.
- If appropriate, conduct interim analysis of efficacy in accordance
- Recommend solutions to address problems with study conduct, enrolment, and sample size and/or data collection.

Study visits (scheduled and unscheduled visit codes)

The total duration of the study is 18 months; follow up period is up to 12 months. The participant has a baseline visit (00.0) and is followed up at month 6 (168 days \pm 14 days) visit code 01.0, last visit is at month 12 (336 days \pm 14 days) visit code 02.0.

The participant might return at the clinic due to an illness, or repeat blood draw, this interim visit codes will be numbered sequentially from the previous scheduled visit. (00.01, 00.02 if its next to the baseline, if next to second visit, the code will be 01.01, 01.02 etc., if its next to last visit it will be coded 02.1, 02.2, etc.).

The study visit window is 2 weeks (14 days), beyond this period a visit code denoting an interim visit is given; e.g. Visit code 01.1 first contact with patient past visit 01.0 and 01.2 denotes second contact with patient past visit 01.0.

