A cost analysis of the intervention from a governmental perspective will be performed. The principle of marginal costing will be used to cost the resources utilised in the alternative strategies. All costs of a historical nature, the sunk costs such as resources invested in buildings, equipment, and vehicles will be ignored. Only costs related to the future, from the onset of the study, will be recorded.

[figure not shown]
Sources of cost information: The following costs will be assessed and classified under direct or indirect cost: Sources of cost data will be; program/ project documents, financial records.

Capital costs:

I. System Costs:

- Software monthly hosting (internet, cloud hosting, call bills,)
- Support maintenance
- Hard ware
 - Computers
 - Internet modem

Recurrent costs:

- I. Supplies (blood collection tubes, vacutainer holders, needle, cotton swabs)
- II. Transport to fro (clinic visit):
- III. Staff/ personnel salaries:

Induced costs:

- I. Transport costs
- II. Number of sick visits attended outside the clinic costs/fees incurred
- III. Airtime fees

Health outcomes:

The number of patients with viral suppression (<1000 copies) will listed per study arm at month 6 and 12, and these will be compared across arms.

Analysis:

Primary outcome measure will be Cost for mHealth Intervention.

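### The Objective 2 analysis never specifies the randomised comparison: arm has no guaranteed place in the model, and no test, effect measure or confidence interval is tied to it

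*Combined protocol and SAP*

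**What the plan says.** The comparison is set up clearly. Section 3.4 (Study Objective 2) describes a randomised trial of standard of care against CFLU plus standard of care. Section 2.6 gives the hypothesis: "using viral load suppression as a proxy measure for ART adherence we anticipate an increment of 15" per cent. The sample size calculation takes 79% and 94% suppressed, two-sided 5% significance and 80% power, and arrives at 93 per arm, raised to 103 per arm for 10% loss. The third specific objective in section 1.3.2 is "To evaluate effect of the mHealth CFLU tool on ART adherence at months 6 and 12".

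The analysis text for the same objective reads differently:

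- **Bivariate Analysis** uses Pearson chi-square tests and odds ratios to examine "The relationship between independent variables (age, gender, ART duration, marital status, education status, occupation and religion) and adherence and virological suppression". Then: "Variables found to be significant at p value of p ≤ 0.05 will be considered for the multivariable analysis".
- **Multivariate Analysis** uses logistic regression to find influencing factors. Besides the variables that pass the screen, "those considered to have a scientific explanation will be entered into the multivariable model". Odds ratios and confidence intervals are promised for the findings in general. The section closes: "After the final model, significant factors for ART adherence/ viral suppression will be computed".

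On analysis by arm, there is "time to viral suppression with survival analysis curves drawn for both arms" under Data Management Analysis Plan. Under the Objective 3 costing, the numbers suppressed "will listed per study arm at month 6 and 12, and these will be compared across arms". The outcome list also gives a different adherence source for each arm, and a CONSORT diagram is planned. None of these names a method for comparing the arms.

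Viral load is measured at baseline and at months 6 and 12 (Data collection procedures). Section 3.3 admits both ART-naïve youth and youth on ART since June 2019.

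**The concern.** Someone following the analysis text literally could finish it without producing the estimate for which 206 young people were randomised. The seven listed variables are participant characteristics, and arm is not one of them. The scientific-rationale route would admit arm, but it names no variable and leaves the decision until the data have been seen.

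Three things are at stake:

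- **Whether the main result appears.** If arm is treated like any other candidate, its adjusted effect is shown only when it is already significant, and effects selected that way are too large on average. A null or modest result, which is equally informative, would drop out of the final model.
- **What it is adjusted for.** The other covariates depend on which happen to pass p ≤ 0.05 in this sample. With seven unrelated variables and independent tests, the chance that at least one passes by luck is 1 − 0.95⁷ = 30%.
- **When it is measured.** With months 6 and 12 on equal footing, the time point can be chosen after the event.

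A smaller point is that baseline viral load is likely to predict later suppression in a mixed naïve and treated population, and it is already collected, yet no stated model uses it. ART duration is listed, but it captures baseline viral load only in part and is itself subject to the screen.

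**Working it through.** **1. The plan's own figure.** Inputs from the sample size calculation are p₁ = 0.94, p₂ = 0.79, 1:1 allocation, two-sided α = 0.05 and 80% power. With p̄ = 0.865 and q̄ = 0.135, the Kelsey formula gives

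n = (1.960 + 0.842)² × 0.865 × 0.135 × 2 / 0.15² = 81.5 per arm.

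The three methods give 82, 81 and 94 per arm, against 81, 80 and 93 in the plan. Inflation gives 186/0.9 = 207, against 206. These agree closely, and the sample size is not in dispute. What matters is that it was computed for a comparison of two proportions by arm.

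**2. If arm goes through the p ≤ 0.05 screen.** This route is assumed, because the documents do not say how arm would enter. The calculation is an exact binomial enumeration with 93 per arm, 79% suppressed in control, and a Pearson chi-square test at 0.05.

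| True difference | Kept | Dropped | Mean observed if kept | Mean observed if dropped |
|---|---|---|---|---|
| +15 (planned) | 87.5% | 12.5% | +16.1 | +7.1 |
| +10 (assumption) | 46.3% | 53.7% | +14.5 | +6.1 |

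The rows average back to the truth: 0.875 × 16.1 + 0.125 × 7.1 = 15.0, and 0.463 × 14.5 + 0.537 × 6.1 = 10.0. Inflation among kept estimates is 16.1/15 = 1.07-fold at the planned effect and 14.5/10 = 1.45-fold at +10.

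**3. The smallest benefit that would pass.** Take 73/93 suppressed in control (93 × 0.79 = 73.5).

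- 83/93 in the intervention arm: difference 10/93 = 10.8 points, pooled proportion 156/186 = 0.839, standard error √(0.839 × 0.161 × 2/93) = 0.0539, z = 1.99. This passes.
- 82/93: difference 9.7 points, z = 0.0968/0.0547 = 1.77. This fails.

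So no observed benefit below 10.8 points would pass the screen.

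**4. What a pre-specified analysis would give.** At exactly 94% against 79% with 93 per arm, the half-width of the 95% confidence interval for the risk difference is 1.96 × √(0.94 × 0.06/93 + 0.79 × 0.21/93) = 9.6 points. The odds ratio is 4.16 (95% CI about 1.55 to 11.2).

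**5. Adjusting for baseline suppression.** The documents give no baseline rate. The assumptions are 60% suppressed at baseline, a common odds ratio for arm, and marginal rates of 79% and 94%. The test is the likelihood-ratio test for arm (12,000 simulated trials).

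| Control suppression at follow-up, baseline suppressed vs not | Unadjusted power | Adjusted power |
|---|---|---|
| 85% vs 70% | 87.5% | 88.5% |
| 95% vs 55% | 87.5% | 92.3% (91.0% by stratified CMH test) |

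Both cases average to the planned control rate: 0.6 × 85 + 0.4 × 70 = 79, and 0.6 × 95 + 0.4 × 55 = 79. Under the null, the adjusted test rejected in 5.0% to 5.3% of 6,000 runs. A separate check with 30% to 50% unsuppressed at baseline and a baseline odds ratio of 3 to 6 gave 89% to 91%, against 87% to 88% unadjusted.

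**6. How large a model the data support.** Expected unsuppressed participants are 93 × 0.21 + 93 × 0.06 = 19.5 + 5.6 = 25.1. That is 12.6 per coefficient with arm and baseline suppression only, and 5.0 with five coefficients.

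**The case against.** The strongest reply is that the comparison is under-described but not absent. The plan has a default test (chi-square), effect measure (odds ratio) and interval. The sample size implies a two-proportion comparison, and suppressed counts are to be compared across arms. A sensible analyst would include the randomised intervention on scientific grounds. That is fair as a guess at intent, but none of this wording links the methods to arm. The across-arm comparison sits under costing without a method, and an implied test fixes no time point or analysis set.

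A second reply is that the screening figures assume a route the plan does not state. They are hypothetical, and the dropped proportions are simply one minus power. If arm were screened, the bivariate table would still show its odds ratio and only the adjusted estimate would be lost. At the planned effect the inflation is small. All of this stands, but the main defect does not depend on those figures.

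A third reply is that baseline adjustment is optional, because randomisation makes the unadjusted comparison valid. This also stands: the gain is about 1 to 5 points of power and rests on assumed baseline rates. Adjustment also changes what the odds ratio means. In the 95%/55% case, a conditional odds ratio of about 5.2 corresponds to the marginal 4.2 used for sizing. Reporting a standardised risk difference alongside it deals with this.

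**Conclusion.** The concern holds and should be fixed before the analysis. The trial was designed and sized for a contrast that its analysis text does not guarantee to estimate. This reading comes directly from the documents and needs no assumption. The size of the harm depends on how arm is handled. If it is kept by judgement, the loss is one of pre-specification. If it is screened, with 93 per arm and 79% control suppression, the adjusted effect is missing from the final model in 12.5% of trials at +15 points and in 54% at an assumed +10, with survivors overstated 1.07-fold and 1.45-fold. The missing baseline adjustment is secondary and would not on its own require a change.

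**What to change.** Add a short primary-analysis paragraph to section 3.4, Study Objective 2:

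- **Outcome and time point:** viral suppression below 1000 copies/mL at one visit named in advance. The sponsor chooses month 6 or month 12 and labels the other secondary.
- **Participants:** analysed in the arm to which they were randomised.
- **Model:** logistic regression with arm always included and baseline suppression (yes/no) as a fixed covariate, without p-value screening. Keep to these two terms, or very few more, given about 25 expected unsuppressed participants.
- **Reporting:** the odds ratio, and the risk difference by marginal standardisation from the same model, each with a 95% confidence interval whatever the p-value.
- **Missing viral loads:** a rule stated in advance, since 10% loss is planned, with a sensitivity analysis counting missing as unsuppressed.

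Keep the screened risk-factor model as a separate exploratory analysis with arm included.

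The cost is protocol or SAP wording and a few lines of Stata (logistic, then margins). No new data are needed. The sponsor gives up the freedom to choose between time points later, and the demographic screening becomes exploratory.

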7. Date of Birth ____/____/____ 1995	8. Gender  Male  Female	9. Ethnicity (Tribe) _____																			

Section C: Social Assessment

11. Known HIV test results?

- Positive
- Negative.

12a) Previous VL test results (N/A if initiating ART)

--	--	--	--	--	--

12b) Date of test results

13. Do you have a partner?

No(if no, go to 14)
 Yes

13 a. If Yes, for how long have you been with your partner

(Yrs., Months)

11a. If positive are you receiving ART treatment?

Yes
 No

11b. If yes, list ART start dates

J. J. —

DD/MM/YYYY

11c: ART Regimen: (Use MoH Codes)

[figure not shown]
--	--	--

14. Have you shared your test results with any
one? Yes No

14. If yes, with who? List relationship

[figure not shown]
a) -----

b) -----

Section D: Education Living Standards

1. Highest level of Schooling Completed
 
 No Formal Education.
 
 P1-P4
 
 P5-P7
 
 S1-S4.
 
 S5-S6
 
 Technical/ University
	
2. Are you currently working?
 
 Yes  No
 
2a. If yes what is your current occupation?

3. What is your household income /month?
 
(Consider ALL sources of income, self or guardian)
 
 Less than 50,000
 
 50,000/= and 100,000
 
 100,001/= and 500,000
 
 500,001/= and 1,000,000
 
 Above 1,000,000
 
 Declined to answer
	
4. Number of people supported on income?
 
 

5. Number of Children  <18 in household (# each age)
 
1. 0-4 Years 
 
2. 5-9 Years 
 
3. 10-14 Years 
 
4. 15 –18year 
	
6. Housing Description
 
 Mud floor walls with no ventilation
 
 Mud floor brick walls with one small window
 
 Brick house with enough windows
 
 Brick house with enough glass windows and well ventilated
 
 Other(Camp, Unipot etc)

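### Age and ART duration are screened by chi-square with no cut points fixed: a cut costs power for a linear age trend, while for ART duration it may cost much, little or nothing

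*Combined protocol and SAP*

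**What the plan says.** All of this is in section 3.4, Study Objective 2, under General data analysis, unless stated otherwise.

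- **Screen.** Seven factors stand in one list: "The relationship between independent variables (age, gender, ART duration, marital status, education status, occupation and religion) and adherence and virological suppression". For all seven the method is the same, a two-way comparison "made using cross tabular analysis and associations investigated using the Pearson Chi-square test". The formula is defined on groups: "r is the number of categories of the ith explanatory variable".
- **Odds ratios.** The next step adds odds ratios for each factor, without saying whether numerical factors are cut or left as measured.
- **Entry rule.** "Variables found to be significant at p value of p ≤ 0.05 will be considered for the multivariable analysis". The Multivariate Analysis paragraph adds a second route: "those considered to have a scientific explanation will be entered into the multivariable model". No variables are named for that route.
- **How the data are held.** The demographic form (Appendix viii) records date of birth and, for those on treatment, asks "If yes, list ART start dates". The Data Management Analysis Plan also takes start dates from the Ministry of Health card.
- **Splits elsewhere.** The focus groups split age at 18 or under versus over 18, and ART at 3 months. Table 1 reports programme data for ages 15-19 and 20-24. None of these is assigned to the trial analysis.
- **Numerical data.** The Univariate Analysis paragraph summarises numerical and categorical data differently. The bivariate step does not keep that distinction.

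**The concern.** A cross-tabulation can use age and ART duration only as categories. Cutting a measured variable discards the ordering within each group, so a steady trend is harder to detect. Because no cut is fixed, the analyst must choose one, possibly after seeing the outcome. At stake is which factors pass the p ≤ 0.05 screen, and hence which may be reported as significant in the final model. The plan already uses logistic regression, which takes both variables uncut.

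**Working it through.** **Reproducing the plan's figure.** The sample size calculation assumes 79% versus 94% suppressed, two-sided 5%, 80% power and equal arms. Exact inputs give 82, 81 and 94 per arm (Kelsey, Fleiss, Fleiss with continuity correction) against the stated 81, 80 and 93. With the odds ratio rounded to 4.2, p1 = 0.79 × 4.2 / (1 + 0.79 × 3.2) = 3.318 / 3.528 = 0.9405, which gives exactly 81, 80 and 93. Then 93 × 1.10 = 102.3, rounded up to 103 per arm, or 206. The plan gives no power or error rate for the screen.

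**Inputs used here.** N = 2 × 93 = 186, and suppression (79 + 94)/2 = 86.5%. The following are assumptions, not in the documents: a slope of 0.6 log odds per SD; age uniform from 15 to the 25th birthday; ART duration either uniform over 0-36 months with nobody naive, or one third naive (zero) and the rest uniform over 0-30 months; the effect either linear on the logit scale or rising to 6 months and then flat.

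**Tests.** For a continuous term, T = [Σ(x − x̄)(y − ȳ)]² / [ȳ(1 − ȳ) Σ(x − x̄)²], compared with 3.84. For a two-group cut, x is replaced by the group indicator, which gives the uncorrected Pearson chi-square. Months plus a naive indicator is tested on 2 degrees of freedom.

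**Power from simulation (4,000 or more trials per scenario where the count was recorded; ranges are across separate runs):**

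| Variable and assumed truth | Single linear term | Months + naive indicator | Two-group cut |
|---|---|---|---|
| Age, linear | 75-77% | – | 62-66% (cut at 18, 19 or 20) |
| ART, uniform 0-36, linear | 76-77% | – | 34-37% (3 months) |
| ART, one third naive, linear | 68-70% | 58% | 55-56% (3 months) |
| ART, one third naive, plateau from 6 months | 67% | 68% | 79% (3 months) |
| ART, uniform 0-36, plateau from 6 months | 62% | – | 90% (3 months) |

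In the third row the 3-month cut loses about 69 − 56 = 13 points against the linear term (12 to 15 across runs), but only 58 − 56 = 2 (at most 3) against months plus the indicator.

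**Hand check for age.** A uniform variable cut at fraction c keeps 3c(1 − c) of the information on a linear trend. The split at 18 or under versus over 18, in completed years, is a cut at the 19th birthday: c = 4/10, keeping 0.72. The 15-19/20-24 split has c = 0.5, keeping 0.75. Power of 77% corresponds to (1.96 + 0.74)² = 7.29. Multiplied by 0.72 this is 5.25, with root 2.29 and power Φ(2.29 − 1.96) ≈ 63%. Multiplied by 0.75 it is 5.47, with root 2.34 and power ≈ 65%. Both agree with the simulation.

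**A second calibration.** With the slope set for about 80% power uncut, N of 186 or 206, and age either uniform or weighted 506:816 as in Table 1, the two age splits give 67-70%. With one third naive, the 3-month ART cut gives 62-65%. Leaving age in ten single-year groups is worse, at 41-49%. Expected unsuppressed counts are then only 186 × 0.135 / 10 = 2.5 to 206 × 0.21 / 10 = 4.3 per group, below the usual 5.

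**False positives with no true effect.** Fixed cuts stay at about 5% (4.2-5.8%). Taking the smallest p gives about 10-12% for the best of three cuts, and 12-13% for the best of four age cuts.

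**The case against.** The strongest case against is that this is a coding preference in a secondary analysis. Several parts of it stand.

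- The odds-ratio step sits between the chi-square test and the p ≤ 0.05 rule, and single-variable logistic regression is a usual source of such odds ratios. The text does not exclude uncut terms there, but it does not specify them either; the named test remains chi-square.
- A reader might infer that a real trend missed by the screen is lost from the final model. The scientific-grounds route allows either variable to enter without passing, so the documents do not support that. The route is discretionary, however, and silent on coding.
- A reader might infer that the plan inflates false positives. Nothing in it says cuts will follow the data, and fixed cuts do not inflate error.
- A reader might infer that cutting roughly halves power for ART duration (77% to 37%). That figure needs a population with no naive participants, whereas the study population includes ART-naive youth, and it needs a linear effect.
- A reader might take the focus-group splits as the only ones available. Table 1 supplies a second age split. Natural cuts therefore exist, but the plan does not choose between them.

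**Conclusion.** The point holds, as a minor one. The plan names a method that forces two variables recorded as dates into unspecified groups. For age with a linear effect, the cost is about 10 to 15 points of power under the stated assumptions. For ART duration no single figure is defensible: the result runs from a large loss (uniform 0-36 months, linear), through about 13 points against a linear term and about 2 against months plus a naive indicator (one third naive, linear), to a gain for the 3-month cut if the effect plateaus early. Error inflation is conditional on data-chosen cuts. The randomised comparison and the sample size are not affected. The direction of the age result rests on linearity; a true step at the chosen cut would lose nothing.

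**What to change.** Amend the Bivariate and Multivariate Analysis paragraphs as follows.

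1. Screen age by single-variable logistic regression, as a continuous term in years, and carry the same term into the multivariable model.
2. For ART duration, pre-specify a continuous form that allows early non-linearity, for example a transformed or spline term with naive participants at zero. Enter it on scientific grounds rather than through the screen. The reason is to avoid relying on one threshold or on a straight line; the power of such a term was not simulated here.
3. Keep chi-square for gender, marital status, education, occupation and religion.
4. Fix any display categories now, choosing between the two age splits already in the document (18 or under/over 18, or 15-19/20-24).

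The cost is a few sentences, with no new data. The downside is a check of shape and possibly one extra degree of freedom.
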